Pre-Specified Study Protocol and Statistical Analysis Plan

Original Project Title: Comparing the Effectiveness of Fatigue Management Programs for

People with MS

Version date of document: November 01, 2019

Clinical Trial Registration: clinicaltrials.gov #NCT03550170

Funding: This work was supported through a Patient-Centered Outcomes Research

Institute (PCORI) Project Program Award (MS-1610-37015). All statements in this report,

including its findings and conclusions, are solely those of the authors and do not necessarily

represent the views of the Patient-Centered Outcomes Research Institute (PCORI), its Board of

Governors or Methodology Committee.

Method and Analysis

Study Design

We are conducting a randomized clinical trial to directly compare three delivery formats of the *Managing Fatigue* intervention. We are using a pragmatic design approach in which 582 participants with MS are being recruited and randomized to teleconference, internet, or in-person versions of the intervention led by a licensed OT. All versions contain the same intervention content but are presented in ways most appropriate to the delivery format. Our goal is to recruit a diverse research sample to examine the effectiveness of each delivery format on different subgroups of participants (i.e., disease, demographic, and psychosocial characteristics). Outcomes are being measured at baseline, two months, three months, and six months. To help facilitate recruitment, the study is being branded as REFRESH (**RE**ducing **F**atigue and **R**estoring **E**nergy to **S**upport **H**ealth).

Sample Size and Inferiority Margin

A sample size of 582 participants is needed to achieve a power of 0.90 for testing the hypothesis and conducting the moderation analyses. Based on previous studies and to err on the side of being conservative, we assumed an attrition rate of 35%, a standardized mean difference of 0.3, a correlation of 0.45 (rho), and a two-sided alpha level of 0.05. An interaction-to-overall effects ratio estimated the extra number of participants needed to examine interactions between delivery formats and participants' baseline characteristics. The prespecified inferiority margin is ten points, which is based on triangulating anchor-based and distribution-based methods to calculate the minimally important difference (MID) on the Fatigue Impact Scale (FIS), and is consistent with a standardized mean difference of 0.3.3-5

Recruitment and Eligibility

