Each participant will be randomized to receive one of the three interventions. Participants are randomized only after availability is confirmed for each delivery format, baseline data collection is complete, and there are enough participants within a specific geographic region (18 to 30 participants) to conduct the group sessions. Permuted block randomization is being implemented. A statistician, who is not involved with data collection or participant interactions, developed a random number table using a 1:1:1 allocation ratio in blocks of six. The statistician directly imported the table into the Research Electronic Data Capture (REDCap)⁸ system to conceal group assignment. REDCap reveals group assignment only after all baseline data are collected and verified by the project manager. Participants are permitted to switch group assignment only when we are unable to provide services (e.g., an OT becomes sick and is no longer able to deliver services or a participant is unable to use a computer).

Masking

As in most behavioral and rehabilitation interventions, direct interaction between participants and OTs is required, making complete masking impossible. To mitigate bias, each OT is delivering only one intervention format, i.e., teleconference, internet, or one-to-one. Data collectors are being masked to group assignment to minimize any biases in baseline or follow-up data collection. We are also measuring the expectations of benefits for each delivery format and conducting sensitivity analyses on measures of treatment fidelity. The study is being described to

participants as a comparison of three courses that could all be equally beneficial for reducing the impact of fatigue.

Intervention Procedures

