Internet. Similar to the teleconference intervention, the internet intervention lasts for six weeks and is group-based; however, unlike the teleconference intervention, participation is asynchronous, with participants able to log on whenever convenient for them. As per the teleconference program, five to ten participants start the intervention at the same time and interact during the intervention, also facilitated by an OT. Participants are given a username and a password to view the intervention content via a secure website. Each week, a new session is activated. Each session includes content delivered via text and short videos, completion of interactive activities and information sharing. OTs facilitate the group discussion boards by responding to entries, asking questions and prompting discussion, and providing encouragement. Website content can be downloaded by participants who wish to have paper copies. To ensure that all participants are able to access and navigate the site, a welcome week session is delivered prior to the first session. However, no intervention content is delivered during this session.

One-to-one, in-person. Unlike the teleconference and internet interventions, the number and length of sessions for the one-to-one, in-person intervention vary over the six-week period. The OT delivers all six topics, but the pace is tailored to participants' needs and preferences.

Thus, although the topics are consistent, OTs can spend more time on those topics that participants find most relevant to them. The participants and OT are instructed to meet at least three times, with at least seven days between sessions. Similar to the teleconference, participants receive a program manual divided into six sections. Sessions are held at a central location or at participants' homes on a day and time convenient for both the OTs and the participants.

Ensuring the Fidelity of the Interventions

Bellg et al.'s¹⁶ recommendation to monitor all aspects of treatment fidelity are being followed. Our goal is to strike a balance between delivering each format consistently, capitalizing on the unique features of each delivery format, and providing OTs with flexibility to deliver the intervention in a way that meets the participants' needs. This balance is needed to maintain internal validity while helping ensure the generalizability of the intervention when implemented under usual circumstances.

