notify the research office immediately if they suspect an adverse event. The participant's physician is informed when additional services are needed for the treatment of an adverse event. Because it is unlikely that these adverse events will be related to the study protocol, an independent Data and Safety Monitoring Board is not being utilized. If a serious adverse event is related to the protocol, the Institutional Review Board and study sponsor will be notified immediately. Quality control checks (e.g., data generation and attrition rate) will occur throughout the study (i.e., every few months) by the statistician not involved in data collection or delivery of the intervention. Concerns about adverse events or quality control checks will be discussed in the monthly team meetings and conveyed to other stakeholder groups convened during the study, including people with MS.

Data will be downloaded from REDCap into a statistical software program. Linear mixed effects model will serve as the primary analysis tool for examining the differential effects of the intervention delivery format on outcomes. The models will include the group assignment variable, time, and interaction of time and group, as well as the subject-specific random intercept and slope for accounting for individual heterogeneity. Using the fitted model, the trajectory of outcomes will be plotted over the study period. Direct estimates of the treatment effect at specific times will be derived by specifying the least squares means for the Treatment × Time interaction. Noninferiority will be established with a 95% confidence interval (CI) using the prespecified margin of inferiority at each time point, which is set at ten points on the total composite score of the FIS. The prespecified inferiority margin for the Multiple Sclerosis Impact Scale is set at eight points for the physical function subscale and six points for the psychological function subscale. These margins are based on anchored-based methods calculated from previous studies.²⁵ ²⁶

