The purpose of the moderator analysis will be to examine the consistency of the intervention's effect across the following subgroups: (1) disability status (i.e., people with moderate to severe disabilities vs. people with mild impairments, (2) race (i.e., Hispanic and non-whites vs. non-Hispanic whites, (3) environment (i.e., people living in rural areas vs. urban areas), and (4) psychosocial characteristics (i.e., people experiencing societal barriers, depression, low health literacy, low social support, and/or low patient activation vs. people without these characteristics). This analysis will involve adding an additional interaction term of group × time × characteristic and the two-way interaction term of time × characteristic and group × characteristic using the mixed effects model that will be used to detect the main treatment effects on fatigue impact.

The purpose of the mediator analysis will be to examine whether changes in self-efficacy and fatigue self-management behaviors influence the relationship between the interventions and outcomes. Significant changes across time in self-efficacy and fatigue self-management behaviors will be evaluated using the proposed mixed effects analysis. Following Hayes et al.,²⁸ the mediation analysis will involve a series of regression analyses to quantify mediation effects using bias-corrected bootstrapped 95% CI.

We will conduct analyses using both intention-to-treat and per-protocol principles. When using intention-to-treat principles, the treatment of missing values will depend on the type of missingness. In the case of missing at random, the proposed mixed effects models should be sufficient. In the case of missing not at random or non-ignorable, a Bayesian method to jointly model response data and missing data will be applied. When using per-protocol principles, participants who provide complete data and attend four or more intervention sessions will be included in the analysis.

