A series of sensitivity analyses are planned to explore how various assumptions and potential confounders might influence the results. Four pre-specified sensitivity analyses are planned: (1) significant differences in time-varying factors between groups after randomization (e.g., exacerbations, changes in medications, or changes in health and wellness services), (2) assumptions of missing data, (3) differences in prespecified margins, and (4) treatment fidelity measures (e.g., attendance, quizzes, and experience of OT). We plan to examine these factors by comparing adjusted to non-adjusted models. Significant differences in time-varying factors between groups after randomization will be entered into the model as covariates during hypothesis testing. We will examine whether any differences exist in results based on how missing data are treated (e.g., missing at random versus missing not at random). We will also use prespecified margins of 4.8 (i.e., standard error of measurement), 15.5 (the mean of 12 anchoredbased MIDs), and 20 (upper limit of the triangulated anchored and distribution-based MIDs). Last, we will assess whether measures of treatment fidelity, such as OT experience and participants' understanding of material, influence outcomes as well as whether differences exist in the per-protocol analysis when participants who provide complete data and attend all six intervention sessions (compared to four and five of the six sessions) are only included in the analysis.

Public and Patient Involvement

Stakeholder groups comprising individuals with MS, policy advocates, insurance representatives, clinicians, and researchers on the project are informing all aspects of the study. This includes drafting and reviewing recruitment and intervention material, branding of the study, selecting which delivery formats to examine, assessing and finding both the ease and

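### The per-protocol set requires complete data, so it becomes a completers analysis: it loses precision and, if dropout differs by arm, is biased in a direction that cannot be known in advance

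*Combined protocol and SAP*

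**What the plan says.** Data Management and Analysis states: "We will conduct analyses using both intention-to-treat and per-protocol principles". For intention-to-treat it adds: "In the case of missing at random, the proposed mixed effects models should be sufficient". The per-protocol set has two conditions: "participants who provide complete data and attend four or more intervention sessions will be included in the analysis". The sensitivity analyses in the same section tighten only the attendance cut, to "participants who provide complete data and attend all six intervention sessions (compared to four and five of the six sessions", and keep the complete-data condition. No planned per-protocol analysis relaxes it. The plan does not say which instruments or visits must be complete.

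The sample-size section says "we assumed an attrition rate of 35" percent.

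On format received, Randomization and Allocation Concealment says: "Participants are permitted to switch group assignment only when we are unable to provide services". The analysis model uses assigned group: "The models will include the group assignment variable, time, and interaction of time and group". Nothing says how a participant who switched is treated in either analysis set.

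The plan does not say whether intention-to-treat or per-protocol decides noninferiority, or whether the two must agree.

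**The concern.** In a noninferiority trial the per-protocol analysis checks whether non-adherence has blurred the arms. It does that only if it differs from intention-to-treat in adherence and in nothing else. Here it also changes the treatment of missing data. Intention-to-treat keeps partial records under the mixed model, and per-protocol discards them.

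Take a participant who attended every session and returned the FIS at baseline, 2 and 3 months but not at 6. That person adhered to the intervention, yet is removed with all three scores. Two things follow. Usable information is lost, and the set is selected on who keeps answering questionnaires. If the two results disagree, the reader cannot tell whether adherence or non-response is the cause. The formats differ in kind (asynchronous web, group telephone, one-to-one in person), so retention that differs by arm is plausible.

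**Working it through.** **Inputs from the document.** 582 participants randomized 1:1:1, so 194 per arm; attrition 35%; standardized difference 0.3; rho 0.45; margin 10 FIS points; 95% confidence interval against the margin at each visit; visits at baseline, 2, 3 and 6 months. Implied SD = 10/0.3 = 33.3.

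**The plan's own figure.** 582 cannot be fully reproduced, because the interaction ratio and the attrition pattern are not given. A single-visit comparison needs 2(1.96 + 1.28)²/0.3² = 234 per arm, 234/0.65 = 360 after attrition, and 1,080 in total. Averaging the three follow-up visits, with attrition spread over them, gives 546 to 570. The point does not depend on 582.

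**Size of the set.** If complete data means the FIS at all four visits, 0.65 × 194 = 126 per arm remain (378 in total) before any attendance exclusion. A wider meaning would leave fewer.

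**Precision, random loss.** Assume equal loss steps over the three follow-ups, so retention per step is 0.65^(1/3) = 0.866. Of 194 per arm, about 26, 22.5, 19.5 and 126 then have 1, 2, 3 and 4 visits.
- Completers: SE = 33.3 × √(2/126.1) = 4.20 at every visit.
- All available data: sum the inverse covariance matrices (compound symmetry, rho 0.45) over these patterns, invert, and take the difference of two arms. SE = 3.59 at month 2 and 3.99 at month 6.
- Variance ratios: (4.198/3.587)² = 1.37 at month 2 and (4.198/3.993)² = 1.11 at month 6.

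**Bias, score-related loss.** Simulation with a true remote deficit of 10 at every follow-up visit. Dropout depends on the last observed FIS score (log-odds 0.5 per SD), visit means are fitted by generalized least squares with known covariance, and noninferiority is declared if estimate + 1.96 SE < 10. There were 1,500 to 3,000 trials per scenario, and repeat runs agreed within simulation error.

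| Assumed loss | Completer estimates, months 2, 3, 6 | False noninferiority, completers |
|---|---|---|
| 45% remote, 25% in person, score-related in both | 7.5, 7.5, 8.2 | 7–9% |
| 35% in each, score-related in remote only | 6.0, 6.0, 7.2 | 10–17% |
| 25% remote, 45% in person, score-related in both | 12.8, 12.6, 11.9 | about 1% or less |
| 35% in each, score-related in person only | 14.0, 14.0, 12.7 | below 1% |
| Equal and equally score-related | no bias | about 2.5% |

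In every row the all-available-data estimates stay near 10, with error near 2.5%.

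A second dropout model, with 35% loss after month 2 depending on the month-2 score, was checked on the month-6 contrast at slopes of 0.5 and 1. Dependence in the remote arm only gave completer error of 5.7% and 10.4%, against 2.6% and 2.7% with partial records kept. Dependence in the in-person arm only gave completer error of 0.9% and 0.4%.

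**Switchers.** Assume that a share s of a remote arm switches, receives the full in-person effect and is kept under the assigned arm. The deficit shrinks to 10(1 − s), and the error is Φ(10s/4.2 − 1.96). At s = 10%: Φ(1/4.2 − 1.96) = 0.043. At s = 2%: Φ(0.2/4.2 − 1.96) = 0.028. A separate month-6 simulation gave 0.031 at 2% and 0.043 at 10%.

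**The case against.** **Direction.** A reader might infer that the rule pushes the trial toward noninferiority. The documents do not support that. They give no attrition by arm, and the mirror scenarios move the completer estimate above 10 and make a false claim rarer. With equal dependence there is no bias.

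**Intention-to-treat runs alongside.** It uses partial records, has a Bayesian joint model for non-ignorable missingness, and has missing-data sensitivity analyses. A false claim would need reliance on the per-protocol result. This stands as a limit on the harm. It does not repair the per-protocol set, because none of those provisions changes the rule, and the plan does not say which set decides.

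**Precision.** The 37% is for month 2, where the penalty is greatest among the follow-up visits. By month 6 it is about 11%.

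**Switchers.** A reader might also infer that the plan keeps switchers in the per-protocol set. That rests on silence. Switching is allowed only when services cannot be provided, availability for every format is confirmed before randomization, and Chromebooks are supplied. Following per-protocol principles is often taken to imply receipt of the assigned format. A move from internet to teleconference would leave the contrast unchanged if both formats carried the same deficit. Excluding switchers is also a selection made after randomization: it could remove, from the internet arm only, people who could not use that format. This part is therefore a request for clarification.

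**Session count.** For the one-to-one format the plan says "The participants and OT are instructed to meet at least three times, with at least seven days between sessions", while the per-protocol rule requires four or more sessions. That is a separate conflict. The change below does not settle it, and the two passages must be reconciled.

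**Conclusion.** The concern holds for the complete-data condition. It turns the per-protocol analysis into a completers analysis and mixes non-response with non-adherence, although the plan itself regards the mixed model as adequate for data missing at random.

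The loss of precision follows from the planned 35% attrition if that loss is random and spread over the visits. The bias is conditional on score-related dropout that differs by arm, and its direction cannot be predicted from the documents. All the dropout patterns are assumptions.

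The figures also assume that complete data means the FIS at every visit, use a compound-symmetry covariance in place of the plan's random intercept and slope, and leave out attendance exclusions. The protection from using all available data holds when dropout depends on observed scores. It would not be assured if dropout depended on unseen ones.

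Switching is secondary: about 3% error at 2% switching and about 4% at 10%, with both rates and the full move to the in-person effect assumed. The change should be made; it does not call the intention-to-treat analysis into question.

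**What to change.** In Data Management and Analysis, delete the complete-data condition from the per-protocol definition and from the six-session sensitivity variant. State that the same mixed model is fitted to every available FIS score of participants who meet the attendance rule. A completers analysis may be kept as a labelled sensitivity analysis, with complete data defined by instrument and visit.

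Add three sentences on switching: participants who switch stay in their assigned arm for intention-to-treat; the per-protocol set requires that the sessions were in the assigned format; and the number of switchers is reported by arm, because excluding them is a selection made after randomization.

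The cost is SAP wording. No new data should be needed: attendance is already documented and each therapist delivers one format, so the format received should be identifiable. A few switchers may leave the per-protocol set, while adherent participants with partial records return to it.

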The authors would like to thank the participants for their time. We also would like to thank [name], [name], [name], [name], [name], and [name] for assistance with intervention refinement and/or development as well as ongoing recruitment, enrollment, data collection, and/or intervention delivery.

Conflict of Interest

[name] has financial relationships with pharmaceutical and devices companies outside the submitted work. The other authors declare that they have no potential or actual conflict of interest pertaining to this research study.

Funding

This work was supported through a Patient-Centered Outcomes Research Institute (PCORI) Project Program Award (MS-1610-37015). All statements in this report, including its findings and conclusions, are solely those of the authors and do not necessarily represent the views of the Patient-Centered Outcomes Research Institute (PCORI), its Board of Governors or Methodology Committee.

Table 1. Schedule of enrolment, interventions, and assessments

Table 1. Schedule of enrolment, interventions, and asses	STUDY PERIOD					
	Enrolment	Allocation	Interventions	Post	t-allo	cation
TIMEPOINT**	-t ₁	0		t ₁	t_2	t ₃
ENROLMENT:			1			
Eligibility screen	X					
Informed consent	X					
In-person assessment	X					
Return baseline questionnaire packet	X					
Allocation		X				
MANAGING FATIGUE INTERVENTION:			I			
One-to-one, in-person			+			
Internet			•			
Teleconference			•			
PRIMARY OUTCOME:			 			
Fatigue Impact Scale ²⁰	X			X	X	X
SECONDARY OUTCOMES:	71			71	71	71
Multiple Sclerosis Impact Scale ²¹	X			X	X	X
Community Participation Indicators ²² 27	X			X	X	X
MODERATORS	21			21	71	71
Multiple Sclerosis Functional Composite ³¹	X					
Medical Term Recognition Test ³²	X					
Neuro QOL – Anxiety ³³	X			X	X	X
Neuro QOL – Sleep ³³	X			X	X	X
Patient Health Questionnaire–8 ³⁴	X			X	X	X
Patient Activation Measure ³⁵	X			71	71	X
Craig Hospital Inventory of Environmental Factors ³⁶	X					- 21
Demographics (i.e., urban/rural and race)	X					
Self-report Comorbidity Questionnaire ³⁷	X					
Modified Social Support Survey ³⁸	X					X
MEDIATORS			I		 	
Energy Conservation Strategies Survey ¹⁹	X			X	X	X
Self-Efficacy for Performing Energy Conservation						
Strategies Assessment ¹⁸	X			X	X	X
Chronic Disease Self-management Scale ³⁹	X			X	X	X
COVARIATES & POSSIBLE CONFOUNDERS						
Sociodemographic (e.g., age, gender, income,	37					
education, living arrangements, and employment)	X					
Godin Leisure-Time Exercise Questionnaire40	X			X	X	X
Adverse events (e.g., exacerbations ⁴¹ and injuries)	X			X	X	X
Health and wellness services ⁴² (e.g., occupational	v					v
therapy, counseling, and prescribed medications)	X					X
Expectation of benefits/Past Experience/Quizzes	X			X		
Satisfaction survey (open- and close-ended questions)				X		
Symptoms of MS Scale ⁴³	X			X	X	X
Neuropsychological Screening Questionnaire44	X					

Key: $t_1 = 2$ months; $t_2 = 3$ months; $t_3 = 6$ months
